### **Drug Accountability**

Drug accountability will be maintained by the principal investigator, who will ensure that a current record of investigational product disposition is maintained and that the investigational product is used only in accordance with the approved protocol.

Patients will be instructed to return all used and unused vials of study drug when they come to the clinic for the final study visit. Adherence with the prescribed regimen for each study drug will be estimated by counting the number of used and unused vials.

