
Based on the safety and tolerability profile of avexitide and the dose-response relationship observed with higher daytime avexitide exposure in the PREVENT trial, we seek to evaluate whether higher dosing regimens of avexitide may confer greater yet protection against hypoglycemia. In addition, given that GLP-1 excursions are also known to occur in forms of HH other than PBH, we seek to evaluate for the first time whether subcutaneous injection of avexitide may provide protection against hypoglycemia in this expanded cohort of patients with HH. Thus, we seek to extend upon the the previously conducted studies by investigating the safety, tolerability and efficacy of avexitide administered as 45 mg BID and 90 mg QD dosing regimens in patients with HH occurring after RYGB, VSG, esophagectomy, gastrectomy, and Nissen fundoplication.

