## INVESTIGATIONAL PLAN

### Study Design

**Overview**—This is a Phase 2b, single center, open-label, cross-over study of avexitide injection in patients with surgically-induced severe, diet-refractory HH. Eligible participants must have a confirmed diagnosis of surgically-induced HH and demonstrate severe, diet refractory HH, as documented by presence of at least two severe hypoglycemia events from which at least one must be characterized by glucose <54 mg/dL as measured by CGM during the 14-day Run-in Period while adhering to medical nutritional therapy.

[figure not shown]
Eligible HH indications include hypoglycemia occurring after:

- Bariatric Surgery:
  - Roux-en-Y Gastric Bypass (RYGB) or Vertical Sleeve Gastrectomy (VSG)
- Upper-Gastrointestinal Surgery:
  - Gastrectomy, Esophagectomy, or Nissen Fundoplication

Provisionally eligible subjects will undergo a 14-day Run-In consisting of standard of care (SOC) treatment (medical nutrition therapy) with standardized mixed meal consumption and screening labs and collection of blood to test for anti-drug antibody (ADA) at the end of the 14-day SOC Run-In to confirm eligibility and establish a baseline within 90 days of randomization. Enrolled participants will be randomized to one of two 14-day avexitide dosing regimen orders (Figure 1). Doses are to be self-administered in the outpatient setting via subcutaneous (SC) injection. Throughout the study duration participants will continue to maintain SOC treatment following standard dietary guidelines for management of PBH and will be evaluated by blinded CGM, patient electronic diary (eDiary) and SMBG. At the end of Treatment Periods 1 and 2, participants will repeat baseline assessments with ADA and trough PK samples additionally drawn. At the end of Treatment Period 2, participants will return used and unused study drug vials during the safety follow-up visit.

**Study Duration**— Depending on when a patient completes the Run-In Period, the maximum anticipated time an individual patient will participate in the study will be ~120 days.

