### **Dispensing and Administration of Study Drug**

Three kits of study drug (two containing 28 x 3mL vials and one containing 6 x 3mL vials of 90 mg/ml solution) will be dispensed by the Investigator on V4. Participants will be given written and oral instructions on how to store, draw up and safely administered study drug. The study drug will be administered as subcutaneous injections either once daily in the morning (90 mg QD), or twice daily (45 mg BID): once in the morning and the second daily dose approximately 12 hours later. During once daily dosing, the morning dosing will occur at least 60 minutes prior to the first morning meal. During twice daily dosing, the morning dosing will not be relative to the timing of the first meal of the day.

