## Study Schedule

The screening period comprises:

- Visit 1 (Zoom): Informed Consent, review of medical history, hypoglycemia questionnaire, concomitant medications, assessment of preliminary eligibility
- Visit 2 (Zoom): training on patient eDiary, glucometer use, and Dexcom G6PRO application and activation. Participants begin 14-day Run-In Period
- Visit 3 (Zoom): Check in with patient.
- On day 10 of the Run-In Period, participants place a new Dexcom G6PRO sensor.
- Visit 4 (SHC): On day 14 of the Run-In Period, participants go to SHC for a urine pregnancy test, an ADA draw, and CMP as applicable then consume a standardized liquid mixed meal over 10 minutes, with fingerstick glucose checks every 30 minutes for a total of 180 minutes. Eligible participants are then enrolled, randomized and dispensed study drug.

Enrolled participants will be randomized 1:1 to one of 2 avexitide dosing regimen orders, and will be trained on study medication injection procedures. Avexitide should be injected subcutaneously either once daily in the morning, or twice daily; once in the morning and the second daily dose approximately 12 hours later. During once daily administration (avexitide 90 mg QD), morning dosing will occur at least 60 minutes prior to the first morning meal. During twice daily administration (avexitide 45 mg BID) morning dosing will not be relative to the timing of the first meal of the day. Throughout, patients will follow currently accepted dietary guidelines for treatment of PBH.

- Visit 5 (Zoom): Participants are trained on study drug injection; initiate Treatment Period 1. Place new Dexcom G6PRO device.
- Day 10 of Treatment Period 1: Participants place a new Dexcom G6PRO device.
- Visit 6 (SHC): On day 14 of Treatment Period 1 participants have a PK and an ADA draw, have their final Treatment Period 1 study drug injection and 90 minutes later consume a standardized mixed meal over 10 minutes, with fingerstick glucose checks every 30 minutes for 180 minutes. Participants are dispensed new study drug and initiate a 2-day washout period.
- Day 4 of Treatment Period 2: Participants place a new Dexcom G6PRO device.

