- Visit 7 (SHC): On day 14 of Treatment Period 2 participants have a PK and an ADA draw, have their final Treatment Period 2 study drug injection and 90 minutes later participants consume a standardized mixed meal over 10 minutes, with fingerstick glucose checks every 30 minutes for a total of 180 minutes. Participants then remove their Dexcom sensor/transmitter and return their used/unused study drug vials.

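### Vials are counted once, after both regimens, so the planned count gives overall adherence and cannot, as written, attribute a shortfall to 90 mg QD or 45 mg BID

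*Combined protocol and SAP*

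**What the plan says.** Under Drug Accountability, "Adherence with the prescribed regimen for each study drug will be estimated by counting the number of used and unused vials". The same section tells patients to "return all used and unused vials of study drug when they come to the clinic for the final study visit". Study Design agrees: "At the end of Treatment Period 2, participants will return used and unused study drug vials during the safety follow-up visit". So does the Visit 7 entry in Study Schedule: "Participants then remove their Dexcom sensor/transmitter and return their used/unused study drug vials". Appendix A marks vial return and study drug accountability in the Visit 7 column only.

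On supply, Dispensing and Administration of Study Drug describes three kits, "two containing 28 x 3mL vials and one containing 6 x 3mL vials of 90 mg/ml solution", which "will be dispensed by the Investigator on V4". Appendix A likewise marks dispensing at Visit 4 only. The Visit 6 entry in Study Schedule reads differently: "Participants are dispensed new study drug and initiate a 2-day washout period". Neither text has anything collected or counted at Visit 6.

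The eDiary and Glucometer section lists hypoglycemia symptoms and outcomes, corrective actions, assistance, diet and glucose values. It lists no record of injections.

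**The concern.** The trial tests one drug in two regimens, and every participant self-administers both at home. The Introduction sets out to study safety, tolerability and "efficacy of avexitide administered as 45 mg BID and 90 mg QD dosing regimens". The primary analysis reports a least squares mean, confidence interval and p-value for each active regimen, and the PK/PD profile of each is an exploratory objective.

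If one regimen looks weaker or less well tolerated, a reader will ask whether participants took less of it. A single count after both regimens does not answer that. Once used and unused vials from both periods have been pooled, the split cannot be reliably reconstructed. What is at stake is the interpretation of the separate QD and BID results.

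**Working it through.** **Inputs from the documents**

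- Vial content (Investigational Product, Dosage and Administration): 0.5 mL x 90 mg/mL = 45 mg.
- Daily use: QD 90/45 = 2 vials in one dose; BID 1 vial x 2 = 2 vials.
- Period length: 14 days per regimen (Study Design).
- Last dose of each period: given at Visit 6 or 7 before the meal test (Study Schedule).

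**Supply.** 28 + 28 + 6 = 62 vials. Full use is 14 x 2 = 28 per period, or 56, plus 6 spares. The stated supply is reproduced.

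**Expected use.** If the day 14 injection at the visit is the last one, no evening BID dose follows it.

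- QD: 14 x 2 = 28 vials.
- BID: 13 x 2 + 1 = 27 vials.
- Total: 55 vials, in either order.

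This assumes that both BID doses are taken on day 1 and that the visit injections come from the participant's own vials. The documents state neither.

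**Illustration.** The documents give no expected non-adherence, so a shortfall of 6 vials is assumed. Overall adherence is 49/55 = 89.1%. If m of the 6 missing vials belong to QD:

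BID minus QD = (27 - (6 - m))/27 - (28 - m)/28

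| m | QD | BID | BID minus QD (points) |
|---|---|---|---|
| 0 | 28/28 = 100% | 21/27 = 77.8% | -22.2 |
| 2 | 26/28 = 92.9% | 23/27 = 85.2% | -7.7 |
| 4 | 24/28 = 85.7% | 25/27 = 92.6% | +6.9 |
| 6 | 22/28 = 78.6% | 27/27 = 100% | +21.4 |

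The rows shown are for QD doses missed whole, two vials at a time. If a QD dose can be taken in part, odd values of m are also possible. The end-points do not change. Each unattributed vial adds 1/27 + 1/28 = 7.3 points to the width of the range.

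**Sensitivity to the denominator.**

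- With 28 vials for BID as well: 50/56 = 89.3% overall, range -21.4 to +21.4 points (6/28).
- With the visit injections not drawn from participant vials, each regimen has 26: 46/52 = 88.5% overall, range -23.1 to +23.1 points (6/26).

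The conclusion is the same in each case.

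**Zero shortfall.** Suppose one QD dose is missed (26 vials used) and two BID vials are spoiled and replaced from the spares (27 + 2 = 29 used). The total is 26 + 29 = 55, exactly as expected, yet QD adherence is 92.9%. A complete count therefore does not guarantee full adherence to each regimen.

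**The case against.** There are four serious arguments on the other side.

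- **The plan may promise nothing by regimen.** The phrase about each study drug may be general wording for overall adherence, and one final count delivers that. This stands. A reader might infer that the plan fails its own stated measure; the text is too ambiguous to support that.
- **No result depends on it.** No planned analysis uses adherence, and no efficacy contrast of QD against BID is stated. This stands too. A reader might infer that the efficacy estimates are biased; nothing in the documents supports that.
- **Other information separates the regimens.** Each 28-vial kit fits one period, the investigator keeps a disposition record, trough PK is drawn at the end of each period, and the dose before each meal test is given at a clinic visit. This stands in part, and it rules out saying that attribution is impossible. But no section assigns a kit to a period or plans a count by kit, and the 6 spares belong to neither. The disposition record is not described as holding doses taken. Trough PK reflects recent doses, and the clinic dose bears on the meal test, not on 14 days of CGM.
- **The shortfall is hypothetical, and the count misses the likelier deviation.** The Missed Doses section lets a missed dose be taken late or with the next one, which leaves no vial unused. This stands: the illustration shows what a count could not resolve, not what is expected to happen, and no vial count will show late or doubled doses.

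The difference between Visit 4 and Visit 6 dispensing is a separate matter and adds no weight here.

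**Conclusion.** The point holds as a low-severity, cheap improvement. Followed exactly, the plan yields one overall adherence figure per participant and no stated means of dividing a shortfall between QD and BID. For an assumed 6-vial shortfall, one participant's adherence difference is undetermined over about 44 points (22.2 + 21.4 = 43.6). That describes what the count leaves open for an individual; it is not an error in any planned estimate. It rests on the assumed shortfall and on the assumptions behind the 55 expected vials, to which the conclusion is not sensitive. The consequence is confined to interpreting the separate regimen results.

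**What to change.** **Preferred.** At Visit 6, after the final Period 1 injection, collect and count all used and unused Period 1 vials before any Period 2 drug is used. Count again at Visit 7 and report adherence by regimen. Mark vial return and accountability at Visit 6 in Appendix A, and align Study Design, Dispensing and Administration, Drug Accountability and Study Schedule. One workable arrangement is a 28-vial kit plus 3 spares at Visit 4 and the same again at Visit 6, which keeps the total at 62; the dispensing row of Appendix A then also needs a Visit 6 mark.

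**Minimal alternative.** Label one 28-vial kit for each period, count by kit at Visit 7, and record the period in which each spare is used.

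**Optional.** Add a short eDiary entry for injection time and number of vials. Only this would capture the late or doubled doses that the Missed Doses section allows.

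**Cost.** A brief count at a visit that is already in person, small wording edits and a few schedule marks; no new visit and no extra vials. If the spares are split, participants have 3 rather than 6 on hand in Period 1. The optional entry adds a little diary burden.

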## **STUDY CONDUCT AND ASSESSMENTS**

### **Screening Procedures**

Patients providing written informed consent will be evaluated to determine eligibility to participate in the study. An initial eligibility review will be conducted, including:

- review of medical history and concomitant medications
- review of Level 2 and Level 3 hypoglycemia event rate (<54 mg/dL by CGM or Level 3 hypoglycemia) during Run-In
- review of clinical lab results

- pregnancy testing (as applicable)

The preliminary eligibility assessments may be performed up to 90 days prior to randomization, consisting of a 14-day Baseline Run-in period during which the following items will be supplied concurrent with training:

- eDiary
- dietary guidelines (describes SOC medical nutrition therapy)
- glucometer, lancets and test strips
- Dexcom G6PRO

## Study Schedule

The screening period comprises:

- Visit 1 (Zoom): Informed Consent, review of medical history, hypoglycemia questionnaire, concomitant medications, assessment of preliminary eligibility
- Visit 2 (Zoom): training on patient eDiary, glucometer use, and Dexcom G6PRO application and activation. Participants begin 14-day Run-In Period
- Visit 3 (Zoom): Check in with patient.
- On day 10 of the Run-In Period, participants place a new Dexcom G6PRO sensor.
- Visit 4 (SHC): On day 14 of the Run-In Period, participants go to SHC for a urine pregnancy test, an ADA draw, and CMP as applicable then consume a standardized liquid mixed meal over 10 minutes, with fingerstick glucose checks every 30 minutes for a total of 180 minutes. Eligible participants are then enrolled, randomized and dispensed study drug.

Enrolled participants will be randomized 1:1 to one of 2 avexitide dosing regimen orders, and will be trained on study medication injection procedures. Avexitide should be injected subcutaneously either once daily in the morning, or twice daily; once in the morning and the second daily dose approximately 12 hours later. During once daily administration (avexitide 90 mg QD), morning dosing will occur at least 60 minutes prior to the first morning meal. During twice daily administration (avexitide 45 mg BID) morning dosing will not be relative to the timing of the first meal of the day. Throughout, patients will follow currently accepted dietary guidelines for treatment of PBH.

- Visit 5 (Zoom): Participants are trained on study drug injection; initiate Treatment Period 1. Place new Dexcom G6PRO device.
- Day 10 of Treatment Period 1: Participants place a new Dexcom G6PRO device.
- Visit 6 (SHC): On day 14 of Treatment Period 1 participants have a PK and an ADA draw, have their final Treatment Period 1 study drug injection and 90 minutes later consume a standardized mixed meal over 10 minutes, with fingerstick glucose checks every 30 minutes for 180 minutes. Participants are dispensed new study drug and initiate a 2-day washout period.
- Day 4 of Treatment Period 2: Participants place a new Dexcom G6PRO device.
- Visit 7 (SHC): On day 14 of Treatment Period 2 participants have a PK and an ADA draw, have their final Treatment Period 2 study drug injection and 90 minutes later participants consume a standardized mixed meal over 10 minutes, with fingerstick glucose checks every 30 minutes for a total of 180 minutes. Participants then remove their Dexcom sensor/transmitter and return their used/unused study drug vials.

## **Study Procedures**

### **eDiary and Glucometer**

Patients will be trained on the use of an eDiary on Visit 2 in which they will record all hypoglycemia signs, symptoms, and outcomes, any corrective actions taken for hypoglycemia, any assistance received related to an episode, and dietary intake. Patients will also receive a glucometer prior to Visit 2 and be instructed to check fingerstick glucose concentrations whenever they experience hypoglycemic symptoms. Patients will also enter into the eDiary all SMBG glucose values obtained during consumption of the 3 standardized liquid meals. Study personnel will train participants on the use of the eDiary and glucometer.

### **Blinded Continuous Glucose Monitoring (CGM)**

During the Run-In phase, a Dexcom Mobile G6 Pro Continuous Glucose Monitoring System in blinded mode (i.e., the CGM device) will be issued to potential study participants. Each participant will be trained on its use in accordance with the manufacturer's instructions. Written instructions for CGM use and maintenance will be provided. The instructions will, if necessary, be repeated at site visits. The data from CGM will be downloaded after Run-In and at the end of each 14-day period for enrolled subjects. Each device will be blinded for use during the study. The Dexcom Mobile G6 Pro CGM System must be removed before magnetic resonance imaging (MRI), computed tomography (CT) scan, or high-frequency electrical heat (diathermy) treatment.

[figure not shown]
### **Dietary Treatment**

All patients will be expected to follow accepted dietary treatment guidelines for PBH throughout the study including during the Run-In period. Guidelines provided include limiting dietary carbohydrates to no more than 30 g per meal or 15 g per snack, avoiding simple, high glycemic index carbohydrates, maintaining adequate protein intake, abstaining from consumption of alcohol, and maintaining post-bariatric vitamin and mineral supplementation. A written description of guidelines will be provided to each participant for at-home reference. The site personnel will be responsible for reviewing the guidelines with patients at each study visit. Patients will report dietary adherence in their eDiary on a daily basis.

### **Mixed Meal Tolerance Test**

At the end of each study period (Run-In, Treatment Periods 1 and 2), participants will consume a standardized liquid meal (e.g., Boost Nutritional Drink) over 10 minutes, with fingerstick glucose checks every 30 minutes for a total of 180 minutes. Participants will record glucose values in the eDiary.

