### **Figure 2**

## Criteria for Evaluation

### ***Primary Efficacy Endpoint***

- The primary endpoint is the baseline-adjusted number of diurnal Level 2 hypoglycemia events (ADA, <54 mg/dL) as measured by CGM and defined as the number of events captured by CGM with glucose measures <54 mg/dL during diurnal hours (8am-10pm) within each treatment period divided by number of days for a given treatment period, then normalized to duration of 14 days. The baseline-adjusted number of diurnal Level 2 hypoglycemia events during 14 days of avexitide treatment (Treatment Periods 1 and 2) and 14 days of standard of care treatment (Run-In Period) will be calculated and examined in a mixed-effect model, including treatment, treatment sequence, treatment period, and surgery type stratum (RYGB vs. Others) as fixed effect, and subject-within-sequence as random effect. The least squares (LS) mean, the standard error (SE), the 2-sided 95% confidence interval (CI), and the p-value will be derived from the mixed-effect model for each active treatment. No multiplicity adjustment is planned, and the primary endpoint will be evaluated through the nominal p-values. P<0.05 is considered statistically significant.

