### ***Secondary Endpoints***

The secondary endpoints include the following:

- Rate of Level 2 hypoglycemia, defined as number of distinct episodes of Level 2 hypoglycemia (SMBG glucose <54 mg/dL), divided by number of days for a given treatment period, then normalized to duration of 14 days.
- Rate of Level 3 hypoglycemia (severe hypoglycemia), defined as the number of severe events during each treatment period characterized by altered mental and/or physical functioning that requires assistance from another person for recovery, divided by number of days for a given treatment period, then normalized to duration of 14 days. This applies regardless of whether a patient actually receives external assistance. Since the categorization of a severe hypoglycemia event can be subjective, particularly in cases where severe neuroglycopenic symptoms/signs occurred and external assistance was needed but was not received, all potential qualifying severe hypoglycemia events will be adjudicated by the principal investigator.
- Percent diurnal time <54 mg/dL, defined as the percentage of CGM values <54 mg/dL during daytime hours (8am-10pm) within each treatment period, normalized to 14 days.
- The magnitude of postprandial hypoglycemia, defined as the glucose nadir as measured by fingerstick glucose occurring within 3 hours of standardized liquid meal consumption. The plasma glucose nadir obtained during avexitide plus standard of care (Treatment Periods 1 and 2) will be compared to during standard of care (Run-In). Particularly, the baseline-adjusted plasma glucose nadir will be calculated for each patient and evaluated.

Secondary endpoints will be analyzed in the same manner as the primary efficacy endpoint.

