### ***Exploratory Endpoints***

- QoL as measured by SF 36 v2, EQ-5D, HSF-II, and HCS.
- Rate of hypoglycemia, defined as the number of distinct episodes of SMBG glucose <70 mg/dL divided by number of days for a given treatment period, then normalized to duration of 14 days.

- Percent time >250 mg/dL, defined as the percentage of CGM values >250 mg/dL during each treatment period, normalized to 14 days
- Percent nocturnal time <54 mg/dL as measured by CGM, defined as the percentage of CGM values <54 mg/dL during nocturnal hours (12am-6am) within each treatment period, normalized to 14 days.
- Number of nocturnal Level 2 hypoglycemia events (ADA, <54 mg/dL) as measured by CGM and defined as the number of events captured by CGM with glucose measures <54 mg/dL during nocturnal hours (12am-6am) within each treatment period divided by number of days for a given treatment period, then normalized to duration of 14 days.

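### Do the CGM and SMBG hypoglycemia endpoints need a rule that leaves out the day-14 meal test?

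*Combined protocol and SAP*

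**What the plan says.** **Timing of the test.** The Mixed Meal Tolerance Test section states: "At the end of each study period (Run-In, Treatment Periods 1 and 2), participants will consume a standardized liquid meal". The Study Schedule places the meal test at Visits 4, 6 and 7, on day 14 of Run-In, Treatment Period 1 and Treatment Period 2. Fingersticks are taken every 30 minutes for 180 minutes. The eDiary and Glucometer section treats these as SMBG values and has them entered in the eDiary; home checks are prompted by symptoms.

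**What the endpoints count.**
- The primary endpoint takes "the number of events captured by CGM with glucose measures <54 mg/dL during diurnal hours (8am-10pm) within each treatment period", scaled to 14 days, and sets results "during 14 days of avexitide treatment (Treatment Periods 1 and 2) and 14 days of standard of care treatment (Run-In Period") side by side.
- The secondary SMBG rate is the "number of distinct episodes of Level 2 hypoglycemia (SMBG glucose <54 mg/dL").
- Percent diurnal time is "defined as the percentage of CGM values <54 mg/dL during daytime hours (8am-10pm) within each treatment period".
- The exploratory endpoints use "the number of distinct episodes of SMBG glucose <70 mg/dL divided by number of days for a given treatment period" and "the percentage of CGM values >250 mg/dL during each treatment period".
- The meal test has its own secondary endpoint, the "glucose nadir as measured by fingerstick glucose occurring within 3 hours of standardized liquid meal consumption".

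None of these definitions mentions the meal test as included or excluded.

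**Sensor wear.** At Visit 7 the sensor is removed after the test. For Period 1, wear follows from the schedule: a device is placed on day 10 and the next on day 4 of Period 2, with no removal listed between. For Run-In it is probable but not stated: a sensor is placed on day 10, and Appendix A lists no removal before the next placement.

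**The concern.** A low provoked by a standardized liquid meal in the clinic is not the same kind of event as a low in daily life. In the treatment periods the test follows an injection by 90 minutes, whereas at home the twice-daily regimen's morning dose is not tied to the first meal. Test fingersticks are scheduled, whereas home fingersticks follow symptoms. If test data are counted, one low can appear in several endpoints at once.

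The response to the test is also likely to depend on treatment: the Introduction reports a higher meal-test nadir and 50% and 75% fewer participants needing rescue on avexitide in the earlier trial. Run-In always comes first, so randomizing the order of the regimens does not protect the contrast with baseline. With few background events, part of the apparent benefit in the event rate could be a meal-test effect already reported through the nadir. If the baseline count happened to stop before the Visit 4 meal, the benefit would instead be understated.

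**Working it through.** The plan gives no event rate, variance or power figure here, so there is none to reproduce. The check asks how far one test per period can move the comparison.

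**Inputs from the documents:** one test per period; 14 diurnal hours (8am–10pm) × 14 days = 196 hours; 180/30 = 6 scheduled checks, usually at most one distinct episode.

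**Assumptions:** *a* = 2, 4 or 10 other events per 14 days off drug; a 60% reduction in these on drug; probability of a test low 0.5 off and 0.25 on drug, or 0.8 off and 0.20 on drug; the test held between 8am and 10pm; baseline adjustment read as a difference, which the plan does not spell out.

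**1. Is the sensor worn in the Period 1 test?** From Period 1 day 10 to Period 2 day 4 is (14 − 10) + 2 washout + 4 = 10 days on one device, so yes.

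**2. The response differs by treatment.** Off drug: *a* + p₀. On drug: 0.4*a* + p₁. Without the test, the difference is 0.6*a* and the relative reduction 60%.

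| a | p₀, p₁ | Off | On | Difference | Share from test | Relative reduction |
|---|---|---|---|---|---|---|
| 2 | 0.5, 0.25 | 2.5 | 1.05 | 1.45 | 0.25/1.45 = 17% | 58% |
| 2 | 0.8, 0.20 | 2.8 | 1.00 | 1.80 | 0.60/1.80 = 33% | 64% |
| 4 | 0.5, 0.25 | 4.5 | 1.85 | 2.65 | 0.25/2.65 = 9% | 59% |
| 4 | 0.8, 0.20 | 4.8 | 1.80 | 3.00 | 0.60/3.00 = 20% | 62.5% |
| 10 | 0.5, 0.25 | 10.5 | 4.25 | 6.25 | 0.25/6.25 = 4% | 59.5% |
| 10 | 0.8, 0.20 | 10.8 | 4.20 | 6.60 | 0.60/6.60 = 9% | 61% |

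The test's share of the absolute difference is visible at 2 events and small at 10. The relative reduction barely moves.

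**3. The response is the same on and off drug.** At *a* = 2 the difference is (2 + p) − (0.8 + p) = 1.2 for any p. Only noise is added. With Poisson counts and independent tests, the variance of the within-person change is 2 + 0.8 = 2.8, plus 2p(1 − p). The SD rises by √(3.30/2.8) = 1.086 at p = 0.5 and √(3.12/2.8) = 1.056 at p = 0.8. At *a* = 10 the factors are √(14.50/14) = 1.018 and √(14.32/14) = 1.011. Overdispersion would make these smaller.

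**4. Baseline omits the test.** With on-drug probability 0.20–0.25, the shortfall is 0.20/1.2 = 17% to 0.25/1.2 = 21% at *a* = 2, and 0.20/6 = 3% to 0.25/6 = 4% at *a* = 10. The text does not point to this case. The Blinded CGM section downloads data after Run-In, the Primary Efficacy Endpoint counts 14 Run-In days, and the Study Schedule lists the Visit 4 meal before enrolment.

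**5. Percent diurnal time.** Thirty minutes below 54 mg/dL during the test adds 0.5/196 = 0.26 percentage points.

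**The case for a change.** The strongest case for a change is that this is an open-label study of up to 20 participants judged at nominal p < 0.05, so a choice about which data count should be settled beforehand, and a sentence would settle it. Low counts are possible, since entry requires only two severe events in Run-In, at least one of them below 54 mg/dL by CGM. A simulation supports the worry: 20 participants, gamma-Poisson counts with between-subject CV 0.6, and a paired t-test of one regimen against Run-In. If the drug has no effect outside the test but cuts test lows by 50% or 75% from a Run-In probability of 0.3–0.9, counting the test gives a significant result favouring drug in 6–50% of trials at 1 background event per 14 days and 3.5–10% at 10. Leaving it out gives 2.1–2.7%, near the nominal 2.5%.

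The silence in the text is real, and the absolute difference can be noticeably larger at low event rates. The rest does not carry. The simulated results are false positives only against an outpatient-only target, which the objectives and endpoints never state. They also need a drug that prevents most lows after a test meal and none after other meals. With a real halving of 5 background events, and test-low probabilities of 0.6 off and 0.15 on drug, the same simulation reaches significance in 96% of trials without the test and 99% with it, so the conclusion is the same.

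The obvious remedy is less clean than it looks. Cutting meal start to 3 hours, with 193 of 196 hours as denominator, cannot apply alike in all periods: Period 2 CGM ends after the test, and no such day-14 removal is listed for Run-In or Period 1. The Level 3 rate would need the same rule.

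**Conclusion.** No change is needed. The missing sentence is a gap that analysts fill sensibly by reading the definitions as they stand: day 14 belongs to each period, so the test counts once in Run-In, once in Period 1 and once in Period 2. Both regimens and the baseline are treated alike. A low prevented during the test is then part of the drug effect on the endpoint as defined.

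The effect is bounded at about one event per 14 days per period and has no fixed direction. Under the stated assumptions, the relative reduction stays at 58–64% with 2 background events and 59.5–61% with 10, against 60% without the test. The absolute difference rises by 0.25–0.60 events. It would matter for interpretation only if mean event rates sat near the entry minimum.

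This rests on assumed event rates and test-low probabilities, a test held between 8am and 10pm, and sensor wear through the Visit 4 meal. Reporting rates free of the provoked test is a legitimate supplementary analysis: stop all counts at the same point before each day-14 test and divide by observed time. It is a choice between two defensible definitions, and the plan is sound without it.
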